6.4.2.1 Exploratory Efficacy Analyses

Summaries of efficacy endpoints may be provided by subgroups defined by demographic and baseline characteristics as appropriate.

6.5 SAFETY ANALYSES

Safety will be assessed through summaries of adverse events, changes in laboratory test results, and changes in selected vital signs. Safety analyses will be performed for treated patients by cohort. Selected analyses will be performed by BCG dose level.

All adverse events with onset on or after treatment on Day 1 (treatment-emergent adverse events) will be summarized by mapped term, appropriate thesaurus levels, and NCI CTCAE v4 toxicity grade. All adverse events, NCI CTCAE v4 Grade ≥ 3 adverse events, adverse events leading to withdrawal of treatment and serious adverse events will be summarized overall and for treatment related events. In addition, all deaths including cause of death will be summarized. All adverse events and deaths will be listed.

All DLTs will be listed for DLT-evaluable patients (see Section 3.1.3 for a definition of DLT-evaluable patients).

NCI CTCAE v4 Grade 3 and 4 laboratory data will be listed; in addition changes in selected laboratory data will be summarized by grade with use of the NCI CTCAE v4. Selected vital signs and selected laboratory data will be summarized. The incidence of antibodies to atezolizumab will be summarized.

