3.1.2 Study Procedures for All Cohorts

Patients will be required to provide sample tumor tissue showing the presence of CIS, to be obtained within 60 days prior to study entry. Tissue should be submitted as formalin-fixed paraffin-embedded (FFPE) blocks (blocks preferred) or at least 10 unstained slides, with an associated pathology report, for central testing. Patients with fewer than 10 unstained slides available at baseline (but no fewer than five) may be eligible following discussion with the Medical Monitor. The Sponsor may replace patients who are later found to be unevaluable for tumor PD-L1 expression by central testing.

Tumor response assessment via cystoscopy and urine cytology will occur every 12 weeks for the first 2 years, and every 24 weeks thereafter until 5 years, and then yearly.

A mandatory tissue biopsy will be obtained from all patients 6 months after C1D1 of atezolizumab. For patients in Cohort 1A, biopsies should be obtained up to 21 days prior to atezolizumab administration. For patients in Cohorts 1B, 2, and 3, biopsies should be obtained 14–21 days prior to BCG intravesical instillation (e.g., Weeks 10, 22, 46, 70 and 94; see [Appendix 3](#)).

The Sponsor may replace patients who are discontinued from the study before the required tumor biopsy samples are obtained.

At the 6-month timepoint (Week 24 visit), documentation of a complete response (CR) is required to continue on study treatment.

Definition of Complete Response (must meet all 3 criteria):

- Cytology: not positive (see below)
- Upper Urinary Tract Imaging (if performed): normal, or abnormal but supportive of CR (with non-positive selective ureteral cytologies)

- Cystoscopy: bladder appears normal; or bladder appears abnormal but all biopsies are negative; or any grade papilloma, any grade papillary urothelial neoplasm of low malignant potential (PUNLMP), or low grade pTa

Interpretation of Urine Cytology:

- If results are Unsatisfactory, Atypical Cell, Suspicious, or Indeterminate, then assay must be repeated no less than 24 hours and up to 21 days later.
- If the results are again Unsatisfactory or Atypical Cell (2 in a row), then treat as if the result was negative.
- Two consecutive Suspicious or Indeterminate urine cytology specimens require further evaluation by cystoscopy and/or upper tract imaging as deemed appropriate by the investigator

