5.2.3 Adverse Events of Special Interest (Immediately Reportable to the Sponsor)

Adverse events of special interest are required to be reported by the investigator to the Sponsor immediately (i.e., no more than 24 hours after learning of the event; see Section 5.4.2 for reporting instructions). Adverse events of special interest for this study include the following:

- DLTs
- Cases of potential drug-induced liver injury that include an elevated ALT or AST in combination with either an elevated bilirubin or clinical jaundice, as defined by Hy's law and based on the following observations:
 - Treatment-emergent ALT or AST $> 3 \times$ baseline value in combination with total bilirubin $> 2 \times$ ULN (of which $\geq 35\%$ is direct bilirubin)
 - Treatment-emergent ALT or AST $> 3 \times$ baseline value in combination with clinical jaundice
- Suspected transmission of an infectious agent by the study drug, as defined below:
 - Any organism, virus, or infectious particle (e.g., prion protein transmitting transmissible spongiform encephalopathy), pathogenic or non-pathogenic, is considered an infectious agent. A transmission of an infectious agent may be suspected from clinical symptoms or laboratory findings that indicate an infection in a patient exposed to a medicinal product. This term applies only when a contamination of the study drug is suspected.

- Pneumonitis
- Colitis
- Endocrinopathies: diabetes mellitus, pancreatitis, adrenal insufficiency, hyperthyroidism, and hypophysitis
- Hepatitis, including AST or ALT > 10 × ULN
- Systemic lupus erythematosus
- Neurologic disorders: Guillain-Barre syndrome, myasthenic syndrome or myasthenia gravis, and meningoencephalitis
- BCG infection
- Events suggestive of hypersensitivity, infusion-related reactions, cytokine release syndrome, influenza-like illness, *and* systemic inflammatory reaction syndrome
- Nephritis
- Ocular toxicities (e.g., uveitis, retinitis)
- Myositis
- Myopathies, including rhabdomyolysis
- Grade >2 cardiac disorders (e.g., atrial fibrillation, myocarditis, pericarditis)

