5.6 ADVERSE EVENTS THAT OCCUR AFTER THE ADVERSE EVENT REPORTING PERIOD

After the end of the adverse event reporting period (see Section 5.3.1), all deaths, regardless of cause, should be reported through use of the Survival Follow-Up eCRF. In addition, if the investigator becomes aware of a serious adverse event or adverse event of special interest that is believed to be related to prior study drug treatment or study procedure, the event should be reported through use of the Adverse Event eCRF.

5.7 EXPEDITED REPORTING TO HEALTH AUTHORITIES, INVESTIGATORS, INSTITUTIONAL REVIEW BOARDS, AND ETHICS COMMITTEES

The Sponsor will promptly evaluate all serious adverse events and adverse events of special interest against cumulative product experience to identify and expeditiously communicate possible new safety findings to investigators, IRBs, ECs, and applicable health authorities based on applicable legislation.

To determine reporting requirements for single adverse event cases, the Sponsor will assess the expectedness of these events with use of the following reference documents:

- Atezolizumab Investigator's Brochure
- Local prescribing information for BCG (OncoTICE)

The Sponsor will compare the severity of each event and the cumulative event frequency reported for the study with the severity and frequency reported in the applicable reference document.

Reporting requirements will also be based on the investigator's assessment of causality and seriousness, with allowance for upgrading by the Sponsor as needed.

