6. STATISTICAL CONSIDERATIONS AND ANALYSIS PLAN

All analyses will be performed by cohort. Selected analyses may also be performed for all cohorts combined as specified below.

All patients treated with any amount of study drug (atezolizumab or BCG) will be included in all analyses unless specified otherwise.

Analyses of DLTs will be performed on an ongoing basis as described in Section 3.1. Analyses of endpoints related to anti-tumor activity will be performed periodically among patients with sufficient follow-up. Final analyses will be performed after the LPLV has occurred.

Continuous variables will be summarized using means, SDs, medians, and ranges. Categorical variables will be summarized by proportions. The baseline value of any variable will be defined as the last available value prior to the first administration of study treatment.

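### Section 6.5 gives adverse events only as crude proportions by cohort, although time on treatment after Week 24 depends on response; a fixed-window and a time-based summary should be added

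*Combined protocol and SAP*

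**What the plan says.** Section 6.5 states that "Safety analyses will be performed for treated patients by cohort" and that "Selected analyses will be performed by BCG dose level". Events are tabulated by mapped term, thesaurus level and toxicity grade. All events, Grade 3 or higher events, and "adverse events leading to withdrawal of treatment and serious adverse events will be summarized overall and for treatment related events". All events and deaths are listed, and dose-limiting toxicities are listed for evaluable patients.

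The form of these summaries comes from Section 6: "Categorical variables will be summarized by proportions". Neither section mentions a rate per unit of exposure, a fixed onset window or a cumulative incidence of adverse events. Study treatment administration is summarized by cohort in Section 6.2 but is not linked to event counts.

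Section 3.1.2 says that at Week 24 "documentation of a complete response (CR) is required to continue on study treatment". Atezolizumab may then continue to at most 32 cycles or 96 weeks, and BCG to at most 120 weeks. Recurrence, progression or unacceptable toxicity stops treatment earlier.

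Section 5.2.3 defines categories of special interest ("Adverse events of special interest for this study include the following"). Section 6.5 names only one of them, dose-limiting toxicity.

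**The concern.** A crude proportion counts patients with at least one event over whatever time each was treated and observed. Here that time is set partly by efficacy, through a protocol rule and not through chance dropout. A patient without a CR leaves treatment at about Week 24 after 8 scheduled atezolizumab doses; a patient with a durable CR can receive 32. If new events keep arising after Week 24, the crude percentage mixes the hazard with the response rate.

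The direction of the distortion is known. A regimen with few responders looks somewhat safer because its patients left, and one with many responders looks somewhat more toxic because they stayed. Safety and tolerability of the single agent and of the combination is the first-listed objective (Section 2.1), and Section 1.4 says that toxicity tolerated in metastatic disease would not be acceptable here. Readers will look at the cohort columns side by side even though no formal comparison is planned.

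**Working it through.** **The plan's own figures.** The documents give no adverse event rate or safety precision for this trial. Their computed design figures are the exact intervals for CR rates in Tables 11 and 12, and all 11 rows reproduce. For example, 8/20 gives 19.1% to 63.9% (plan: 19%, 64%) and 16/20 gives 56.3% to 94.3% (plan: 56%, 94%). The CR rates of 40% and 80% used below come from those rows; they are illustrative values there, not expectations.

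**Exposure.** Scheduled doses are 8 without a CR and up to 32 with one. Mean doses = 8(1 − CR) + 32·CR, which is 17.6 at CR 40% and 27.2 at CR 80%.

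**Illustration 1.** Assumptions, not in the documents: the same constant hazard h of a first event in every patient; non-responders at risk for 24 weeks, responders for 96.

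Crude incidence = (1 − CR)(1 − e^(−24h)) + CR(1 − e^(−96h)).

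At h = 0.01 the two risks are 21.3% and 61.7%:
- CR 40%: 0.6 × 0.213 + 0.4 × 0.617 = 37.5%
- CR 80%: 0.2 × 0.213 + 0.8 × 0.617 = 53.6%

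| h per week | Through Week 24, any CR rate | Crude, CR 40% | Crude, CR 80% |
|---|---|---|---|
| 0.005 | 11.3% | 22.0% | 32.8% |
| 0.01 | 21.3% | 37.5% | 53.6% |
| 0.02 | 38.1% | 57.0% | 75.9% |

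**Illustration 2, sensitivity.** Assume a 15% risk for a non-responder observed for 24 weeks plus 30 days (28.3 weeks). A responder treated to Week 96 is observed for 100.3 weeks, 3.5 times as long. The hazard is −ln(0.85)/28.3 = 0.00575 per week, or 30.0 first events per 100 patient-years, whatever the CR rate. If r is the responder's risk, the gap between CR 40% and CR 80% is (0.8 − 0.4)(r − 0.15).

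| Late hazard and responder stop | Crude, CR 40% | Crude, CR 80% | Gap, points |
|---|---|---|---|
| Same as early, Week 96 | 26.5% | 38.0% | 11.5 |
| Half of early, Week 96 | 21.4% | 27.7% | 6.3 |
| Same as early, Week 72 | 23.2% | 31.4% | 8.2 |
| Same as early, Week 48 | 19.4% | 23.8% | 4.4 |
| No late events | 15.0% | 15.0% | 0 |

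**Sampling error.** Cohorts 2 and 3 have about 10 patients each, at most 20 with the expansion. The exact 95% interval is 2.5% to 55.6% for 2/10 and 5.7% to 43.7% for 4/20. The distortion is smaller than the uncertainty in any one cohort.

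**The case against.** **Size.** The 16-point gap at h = 0.01 is near the upper end. Week 96 is a maximum, and responders who recur or have toxicity stop sooner. A constant hazard also fits BCG poorly: Appendix 3 schedules 9 instillations before Week 24 and 9 over Weeks 24 to 95, a third of the weekly rate, and Courses 2 to 5 are optional in Cohort 1B. With 0.01 per week early and a third of that later, a responder's risk is 1 − e^(−0.48) = 38.1% and the gap is 0.4 × (38.1 − 21.3) = 6.7 points. For Cohorts 1A and 1B, Table 11 uses observed rates of 40% to 50%; ten CR points at 0.01 per week is 0.1 × (61.7 − 21.3) = 4.0 points, less than one patient in 20. For events of any grade there is almost no room for the effect: 95.8% to 97.9% of patients had one in the metastatic data of Table 3. All of this stands.

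**Comparison.** A reader might infer that comparing safety between cohorts is the study's first objective. Section 2.1 asks only for the safety of the single agent and of the combination. The cohorts are not randomized and differ in disease state, so their rates would not be strictly comparable even at equal exposure.

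**Events of special interest.** A reader might infer that these would appear only as scattered individual terms. Section 6.5 also plans thesaurus-level and grade summaries and full listings. What is missing is one table grouped by the Section 5.2.3 categories.

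**Section 5.7.** It might seem that the commitment "The Sponsor will compare the severity of each event and the cumulative event frequency reported for the study with the severity and frequency reported" in reference documents should move to the new measures. That text concerns expectedness for expedited reporting, and a Week 24 cut would remove later events from it. It should be left alone.

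**What remains.** Reporting exposure in Section 6.2 lets a reader suspect the problem but not correct for it, because event timing is not shown. Small cohorts do not remove a distortion whose direction is known.

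**Conclusion.** The point holds as an interpretability bias. As planned, crude incidence by cohort will tend to rise with the CR rate at an unchanged hazard, provided that events continue after Week 24. The documents do not establish that late hazard, so a flat statement that the cohort with more responders will look more toxic goes too far.

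Across CR rates of 40% and 80%, the gap is 16 points at 0.01 per week with every responder treated to Week 96. On the 15% non-responder risk it is 11.5 points at full hazard to Week 96, 6.3 at half the late hazard, 4.4 if responders stop at Week 48, and zero with no late events. All hazards are assumptions. The gap is below single-cohort sampling error and no between-cohort safety test is planned, so no error rate is affected. This is a cheap improvement to the reporting, not a defect in the design.

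**What to change.** In Section 6.5, for Grade 3 or higher events, serious events, and events of special interest grouped by the Section 5.2.3 categories, add beside the crude percentage by cohort:

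- (a) the proportion of patients with onset in the first 24 weeks, with a note that earlier stops for progression or toxicity still affect it; and
- (b) cumulative incidence of the first event over time, with numbers at risk, or first events per patient-year at risk.

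State when time at risk ends. Section 6.5 gives no end, and for non-serious events Sections 5.3.1 (90 days after last dose) and 5.4.2.2 (30 days) must be reconciled.

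The cost is analysis-plan wording and a few extra tables from dosing and event dates already collected; no treatment rule changes. Patient-year rates assume a roughly constant hazard, which the cumulative incidence display avoids. After Week 24 that display rests almost entirely on responders and should be labelled so.

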6.6 PHARMACODYNAMIC ANALYSES

PD analyses will include assessments of PD biomarkers in both tumor tissue and whole blood. Changes in PD and biomarkers potentially related to outcomes will be listed by dose, cohort, and response status. Change from baseline will be reported descriptively as means, medians, and ranges and as a function of the response.

6.7 PHARMACOKINETIC ANALYSES

Available atezolizumab serum concentrations data (C_{\min} and C_{\max}) will be tabulated and summarized for each course or cycle, as appropriate. Descriptive statistics will include means, medians, ranges, and SDs, as appropriate.

Additional PK analyses may be conducted as appropriate.

6.8 PATIENT-REPORTED OUTCOME ANALYSES

Cycle scores and change from baseline in symptoms, function, and HRQoL, as measured by the EORTC QLQ-C30 and the EORTC QLQ-NMIBC24 will be reported descriptively by cohort as means, SDs, medians, and ranges.

6.9 INTERIM ANALYSIS

6.9.1 Planned Interim Analyses

A preliminary assessment of anti-tumor activity and safety will be performed on Cohorts 1A and 1B prior to initiation of enrollment into Cohorts 2 and 3.

Given the nature of this study, the Sponsor may choose to perform additional periodic analyses of safety or efficacy on any cohort.

7. DATA COLLECTION AND MANAGEMENT

7.1 DATA QUALITY ASSURANCE

The Sponsor will supply eCRF specifications for this study. A contract research organization (CRO) will be responsible for data management of this study, including quality checking of the data. Data entered manually will be collected via EDC with use of eCRFs. Sites will be responsible for data entry into the EDC system. In the event of discrepant data, the CRO will request data clarification from the sites, which the sites will resolve electronically in the EDC system.

The CRO will produce a Data Quality Plan that describes the quality checking to be performed on the data. Central laboratory data will be sent directly to the CRO, with use of the CRO's standard procedures to handle and process the electronic transfer of these data.

The Sponsor will perform oversight of the data management of this study, including approval of the CRO's data management plans and specifications. Data will be periodically transferred electronically from the CRO to the Sponsor, and the Sponsor's

standard procedures will be used to handle and process the electronic transfer of these data.

eCRFs and correction documentation will be maintained in the EDC system's audit trail. System backups for data stored at the CRO and records retention for the study data will be consistent with the CRO's standard procedures.

7.2 ELECTRONIC CASE REPORT FORMS

eCRFs are to be completed through use of the CRO's EDC system. Sites will receive training and have access to a manual for appropriate eCRF completion. eCRFs will be submitted electronically to the Sponsor and should be handled in accordance with instructions from the Sponsor.

All eCRFs should be completed by designated, trained site staff. eCRFs should be reviewed and electronically signed and dated by the investigator or a designee.

At the end of the study, the investigator will receive patient data for his or her site in a readable format on a compact disc that must be kept with the study records. Acknowledgement of receipt of the compact disc is required.

7.3 SOURCE DATA DOCUMENTATION

Study monitors will perform ongoing source data verification to confirm that critical protocol data (i.e., source data) entered into the eCRFs by authorized site personnel are accurate, complete, and verifiable from source documents.

Source documents (paper or electronic) are those in which patient data are recorded and documented for the first time. They include, but are not limited to, hospital records, clinical and office charts, laboratory notes, memoranda, patient-reported outcomes, evaluation checklists, pharmacy dispensing records, recorded data from automated instruments, copies of transcriptions that are certified after verification as being accurate and complete, microfiche, photographic negatives, microfilm or magnetic media, X-rays, patient files, and records kept at pharmacies, laboratories, and medico-technical departments involved in a clinical study.

Before study initiation, the types of source documents that are to be generated will be clearly defined in the Trial Monitoring Plan. This includes any protocol data to be entered directly into the eCRFs (i.e., no prior written or electronic record of the data) and considered source data.

Source documents that are required to verify the validity and completeness of data entered into the eCRFs must not be obliterated or destroyed and must be retained per the policy for retention of records described in Section 7.5.

To facilitate source data verification, the investigators and institutions must provide the Sponsor direct access to applicable source documents and reports for study-related monitoring, Sponsor audits, and IRB/EC review. The study site must also allow inspection by applicable health authorities.

7.4 USE OF COMPUTERIZED SYSTEMS

When clinical observations are entered directly into a study site's computerized medical record system (i.e., in lieu of original hardcopy records), the electronic record can serve as the source document if the system has been validated in accordance with health authority requirements pertaining to computerized systems used in clinical research. An acceptable computerized data collection system allows preservation of the original entry of data. If original data are modified, the system should maintain a viewable audit trail that shows the original data as well as the reason for the change, name of the person making the change, and date of the change.

7.5 RETENTION OF RECORDS

Records and documents pertaining to the conduct of this study and the distribution of IMP, including eCRFs, electronic patient-reported outcome data (if applicable), Informed Consent Forms, laboratory test results, and medication inventory records, must be retained by the Principal Investigator for 15 years after completion or discontinuation of the study, or for the length of time required by relevant national or local health authorities, whichever is longer. After that period of time, the documents may be destroyed, subject to local regulations.

No records may be disposed of without the written approval of the Sponsor. Written notification should be provided to the Sponsor prior to transferring any records to another party or moving them to another location.

Roche will retain study data for 25 years after the final Clinical Study Report has been completed or for the length of time required by relevant national or local health authorities, whichever is longer.

8. ETHICAL CONSIDERATIONS

8.1 COMPLIANCE WITH LAWS AND REGULATIONS

This study will be conducted in full conformance with the ICH E6 guideline for Good Clinical Practice and the principles of the Declaration of Helsinki, or the *applicable* laws and regulations of the country in which the research is conducted, whichever affords the greater protection to the individual. The study will comply with the requirements of the ICH E2A guideline (Clinical Safety Data Management: Definitions and Standards for Expedited Reporting). Studies conducted in the United States or under a U.S. Investigational New Drug application (IND) will comply with U.S. FDA regulations and applicable local, state, and federal laws. Studies conducted in the European Union or

European Economic Area will comply with the E.U. Clinical Trial Directive (2001/20/EC) *and applicable local, regional, and national laws.*

